**F.3 SIGNIFICANT CHANGES TO HUMAN SUBJECTS, VERTEBRATE ANIMALS, BIOHAZARDS, AND/OR SELECT AGENTS****F.3.a Human Subjects**

No Change

**F.3.b Vertebrate Animals**

No Change

**F.3.c Biohazards**

No Change

**F.3.d Select Agents**

No Change

## G. SPECIAL REPORTING REQUIREMENTS

G.1 SPECIAL NOTICE OF AWARD TERMS AND FUNDING OPPORTUNITIES ANNOUNCEMENT REPORTING REQUIREMENTS
File(s) uploaded: FPIRB_FWA_2018.pdf
G.2 RESPONSIBLE CONDUCT OF RESEARCH
Not Applicable
G.3 MENTOR'S REPORT OR SPONSOR COMMENTS
Not Applicable
G.4 HUMAN SUBJECTS
G.4.a Does the project involve human subjects?
Yes
Is the research exempt from Federal regulations?
No
Does this project involve a clinical trial?
Yes
If yes, is this an NIH-defined Phase III Clinical Trial?
No
G.4.b Inclusion Enrollment Data
Report Attached: 'We are here now' - a multi-level, multi-component sexual and reproductive health intervention for American Indian youth
G.4.c ClinicalTrials.gov
Does this project include one or more applicable clinical trials that must be registered in ClinicalTrials.gov under FDAAA?
Yes
If yes, provide the ClinicalTrials.gov identifier, NCT number (e.g., NCT00654321) for those trials: NCT03694418
G.5 HUMAN SUBJECTS EDUCATION REQUIREMENT
Are there personnel on this project who are newly involved in the design or conduct of human subjects research?
No
G.6 HUMAN EMBRYONIC STEM CELLS (HESCS)
Does this project involve human embryonic stem cells (only hESC lines listed as approved in the NIH Registry may be used in NIH funded research)?
No
G.7 VERTEBRATE ANIMALS

Does this project involve vertebrate animals?
 
No
																			

G.8 PROJECT/PERFORMANCE SITES
 
 
 [REDACTED]	
 
 Primary: MONTANA STATE UNIVERSITY - BOZEMAN	625447982	MT-001	[name]	
 
 Fort Peck Community College	102366432	MT-001	[name]	
 
 Fort Peck Assiniboine & Sioux Tribes Language & Culture Dept	106578164	MT-001	[name]	
 
				[REDACTED]				Primary: MONTANA STATE UNIVERSITY - BOZEMAN	625447982	MT-001	[name]	Fort Peck Community College	102366432	MT-001	[name]	Fort Peck Assiniboine & Sioux Tribes Language & Culture Dept	106578164	MT-001	[name]
[REDACTED]																			
Primary: MONTANA STATE UNIVERSITY - BOZEMAN	625447982	MT-001	[name]																
Fort Peck Community College	102366432	MT-001	[name]																
Fort Peck Assiniboine & Sioux Tribes Language & Culture Dept	106578164	MT-001	[name]																

G.9 FOREIGN COMPONENT
 
No foreign component
																			

G.10 ESTIMATED UNOBLIGATED BALANCE
 
G.10.a Is it anticipated that an estimated unobligated balance (including prior year carryover) will be greater than 25% of the current year's total approved budget?
 
Yes
 
Estimated unobligated balance: 666930
 
G.10.b Provide an explanation for unobligated balance: The estimate unobligated balance will be greater than 25% because: 1) Year 1 was truncated by 4 months; 2) there was a new hire that had to be recruited and hired; 3) the subawards were delayed in getting executed because of the time allocated to getting the new hire and the death of 2 elders at Fort Peck during the Summer of 2018.
 
G.10.c If authorized to carryover the balance, provide a general description of how it is anticipated that the funds will be spent The carryover funds will be used to complete the following:
 
 
* Hold monthly team meetings and quarterly CAB meetings. When necessary, we will meet with CAB members individually.
 
* Continue monthly trips to Fort Peck.
 
* Recruit, hire, and train staff in Native Stand and Native Voices; identify the cultural mentors; purchase all necessary materials and supplies.
 
* Collect baseline data from March 1, 2019 to June 1, 2019 as originally planned in Year 1.
 
* Upon completion of the baseline data collection randomize the 5 schools for participation in the intervention.
 
* Analyze baseline data collection in collaboration with the CAB.
 
* Implement evaluation of the systems level intervention with the Fort Peck Epi Team.
 
* Start the implement of the full intervention in 1 school beginning September 1, 2019.
 
* Establish DSM Committee and hold 2 meetings.
 
* Establish contracts with study consultants.
 
																			

G.11 PROGRAM INCOME
 
Is program income anticipated during the next budget period?
 
No
																			

G.12 F&A COSTS
 
Is there a change in performance sites that will affect F&A costs?
																			

No

---

FWA#: **FWA00019355**  
Institution: **Fort PeckCommunity College**  
Expires: **06/20/2023**

OMB No. 0990-0278  
Approved for use through July 31, 2020

#### **Institutional Components**

List below all components over which the Institution has legal authority that operate under a different name. Also list with an asterisk(\*) any alternate names under which the Institution operates.

NOTE: The Signatory Official signing this Assurance must be legally authorized to represent the Institution providing this Assurance and all components listed below.

Name of Component or Alternate Names Used	City	State (or Country if Outside U.S.)	
Fort Peck Community College IRB 1/1	Poplar	MT	A

#### **3 Statement of Principles**

This Institution assures that all of its activities related to human subjects research, regardless of the source of support, will be guided by the following statement of principles governing the institution in the discharge of its responsibilities for protecting the rights and welfare of human subjects of research conducted at or sponsored by the institution. (indicate below)

***The Belmont Report***  
***The Declaration of Helsinki***

#### **4. Applicability**

(a) This Assurance applies whenever this Institution becomes engaged in human subjects research conducted or supported by any U.S. federal department or agency that has adopted the U.S. Federal Policy for the Protection of Human Subjects (also known as the Common Rule), unless the research is otherwise exempt from the requirements of the Common Rule or the department or agency conducting or supporting the research determines that the research shall be conducted under a separate assurance.

(b) Optional: This Institution elects to apply the following to all of its human subjects research regardless of the source of support, except for research that is covered by a separate assurance:

*The Common Rule and subparts B, C, and D of the HHS regulations at 45 CFR part 46*

**5, Assurance of Compliance with the Terms of the Federalwide Assurance**

(a) This Institution assures that whenever it engages in research to which this Assurance applies, it will comply with the Terms of the Federalwide Assurance (contained in a separate document on the Office for Human Research Protections (OHRP) website).

## **6, Designation of Institutional Review Boards (IRBs)**

This Institution assures that it will rely upon only IRBs registered with OHRP for review of research to which this FWA applies. This institution (a) designates the following internal IRB(s) for review of research under this Assurance; or (b) does not have an internal IRB and designates the following external IRB for review of all research to which this FWA applies or, if multiple external IRBs are relied upon, the following external IRB that reviews the largest percentage of research to which this FWA applies.

NOTE: Institutions designating internal IRBs do not need to designate any of the external IRBs upon which it relies.

HHSIRB Registration Number	Name of IRB as Registered with HHS	Is the IRB Internal or External to the Institution?
---	---	--

**Planned Enrollment**

Racial Categories	Ethnic Categories									Total	
	Not Hispanic or Latino			Hispanic or Latino			Unknown/Not Reported Ethnicity				
	Female	Male	Unknown/Not Reported	Female	Male	Unknown/Not Reported	Female	Male	Unknown/Not Reported		
American Indian/Alaska Native	500	500		0	0					1000	
Asian	0	0		0	0					0	
Native Hawaiian or Other Pacific Islander	0	0		0	0					0	
Black or African American	0	0		0	0					0	
White	4	4		0	0					8	
More than One Race	0	0		0	0					0	
Unknown or Not Reported											
Total	504	504		0	0					1008	

**Cumulative Enrollment**

**NOTE:** No cumulative enrollment data exists. Although prompted to do so, the PD/PI did not enter information. No data can be displayed.

## Introduction

This survey will ask you questions about yourself. Many of the questions are about topics related to sex, alcohol and drugs, how you talk to your parents about sex, and your life experiences. Please remember that all of your answers to the questions are anonymous. This means that no one will know that it was you who answered these questions. No one will know your name and your answers to the questions. Only the answers to the questions will be recorded, not your name.

Thank you for taking the time to complete this survey.

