**For the student and parent/legal guardian participating in *NIE*, there are 2 forms of data collection:** a student survey and a parent/legal guardian survey. [name], a part-time assistant, and the N/E school outreach coordinator will oversee both surveys' administration. The student surveys and parent/legal guardian surveys will be completed using Research Electronic Data Capture or "REDCap." REDCap is a secure web application for building and managing surveys and databases.

The students and parents will take the survey on iPads that have the mobile application version of REDCap installed on the tablets. The mobile app version of REDCap collects data offline to be uploaded to an online, secure database once a secure wifi location is reached. Deidentified data will be stored virtually on the REDCap server and available for download to [name], [name], [name], [name] and [name]. Only [name], the *NIE* outreach coordinator, and [name] will have access to names linking students and parents to their records during data collection and intervention implementation. These files will be kept in a locked file cabinet by [name] at MSU after data collection.

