## **SECTION 5: SELECTION AND ENROLLMENT OF PARTICIPANTS**

**4.1 Inclusion Criteria.** To be eligible for inclusion in *N/E*, students must be: 1) 15 to 18 years old; 2) a registered member of a federally recognized tribe or an associate tribal member; and 3) a resident of Fort Peck with a parent/legal guardian. For inclusion in the systems-level component of *N/E*, only those staff members who sit on the Epi Team as representatives of their respective agencies are eligible. Written informed consent will be obtained from the head of each agency represented on the Epi Team and the staff member participating in the Epi Team.

**4.2 Exclusion Criteria.** Exclusion criteria are minimal due to the CAB's value of inclusion in *N/E*. Exclusion criteria include: 1) not meeting the aforementioned inclusion criteria; and 2) having a medically identified physical or cognitive impairment that would impede their understanding of and participation in the educational content and activities of *Native Stand*, *Native Voices*, and the cultural mentoring program.

**4.3 Study Enrollment Procedures.** Students and their parent/legal guardian will be recruited from each of the study's 5 schools. Based on discussions with school personnel and our previously successful recruitment strategies, recruitment will occur via flyers posted in the schools, letters to the parents, parent-teacher meetings, and word of mouth. Additionally, a parent/legal guardian session that provides an overview of *N/E*, the content and format of the intervention components, and risks and benefits of participation will be held at each of the study's 5 schools. Students and their parents/legal guardians, and students from each cluster, will be recruited for participation at baseline. Students and their parents/legal guardians will be recruited for baseline participation **prior to randomization of the sites**. Students and parents/legal guardians will be assigned unique study identification numbers. No persons who refuse to participate in the study, in whole or in part, will be coerced to engage in any study activity. After written consent and assent is obtained from the parent/legal guardian and child, respectively, they will be enrolled in the study.

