**B. Confidentiality and Data Safeguards:** To ensure confidentiality, all information will be coded using a unique identification number so that it cannot be associated with any individual. All of the survey data will be labeled with study identification numbers and stored separately from the informed consent forms in a locked file cabinet in [name]'s locked office at Fort Peck Community College. A master sheet, with individual names and their respective unique study identification numbers, will be kept in a separate locked file that can be accessed only under supervision of the PI or Project Director. The data collection from the student surveys and parent/legal guardian surveys will be downloaded using the RedCap software into the MSU Box server, a file-sharing cloud server, for storage. This is a password protected virtual storage system for de-identified research materials that only specified invited individuals (members of the research team) may view. The audiotapes of the focus groups will be stored separately from the informed consent forms in a locked file cabinet in [name] locked office at Montana State University. All other focus group data including the de-identified transcripts, interview summaries, and the results of the content analysis will be stored on the MSU Box server. All data entered into Box as part of the project's computerized database will be identified by unique identification number only. The entire research team and all other project personnel who come in contact with data or with the human subjects of the intervention will sign a formal oath of confidentiality. The information gathered will be used only for scientific, program evaluation, or instructional purposes. No information about the identities of study participants will be published or presented at conferences.

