- **Suicide thoughts or attempts:** Two types of risks will be addressed in the project: (a) ideation or presentation of thoughts or interest in suicide, and (b) action, which includes both thoughts of suicide as well as the presence of a plan and means to accomplish a suicide act. As participants complete the data collection instruments, key personnel will review instruments and items for response values that indicate concern. Based on the response values, these key personnel will collectively review disclosed information and, if deemed necessary, conduct follow-up inquiry with the participant to further determine level of risk. If the participant is determined to present immediate risk, a referral will be made to one of the following, depending on which is most appropriate for the situation: IHS Poplar Service Unit, IHS Wolf Point Service Unit, or Fort Peck Tribes' Health Promotion and Disease Prevention Program, which offers mental health services to youth in schools. If the disclosure is the result of one of the written items on the data collection tools, [name] will contact the participant by telephone. If the disclosure occurs during an on-site session, the session leader will follow through with an in-depth interview to clarify the presence of suicidal risk and develop a plan of action. Session leaders and mentors will be trained and required to identify suicidal risks in both the domains of ideation and action. Session leaders will follow up in the same way and inform the PI. In the most extreme cases of risk, the PI then assumes follow-up responsibility for the plan of action.

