- b. Have you often worried that you have made a mistake or done something the wrong way?
  - i. No
  - ii. Yes
- c. Have you been almost always worried about something?
  - i. No
  - ii. Yes
- d. Have you been very worried about whether other people like you?
  - i. No
  - ii. Yes
- e. Have you often gotten worried or nervous?
  - i. No
  - ii. Yes

YOU ARE FINISHED WITH THE SURVEY! THANK YOU VERY MUCH FOR TAKING THE TIME TO COMPLETE THE SURVEY. PLEASE REMEMBER THAT NONE OF YOUR RESPONSES WILL BE ASSOCIATED WITH YOUR NAME. IF YOU HAVE ANY QUESTIONS ABOUT THIS SURVEY PLEASE ASK US.

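### The student survey promises strict anonymity, but the protocol links answers to names and has staff act on them, so the survey wording must be corrected

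*Combined protocol and SAP*

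**What the plan says.** The Introduction to the student survey tells the student: "Please remember that all of your answers to the questions are anonymous". It then defines the term: "This means that no one will know that it was you who answered these questions". It adds that names are not recorded. The closing text, after the feelings and emotions items, repeats the assurance: "PLEASE REMEMBER THAT NONE OF YOUR RESPONSES WILL BE ASSOCIATED WITH YOUR NAME".

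The protocol describes a different arrangement.

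- Section 5, item 4.3 (enrollment): "Students and parents/legal guardians will be assigned unique study identification numbers".
- Section 4.1: a small set of staff "will have access to names linking students and parents to their records during data collection and intervention implementation".
- Section 7, item 2.B (confidentiality): "A master sheet, with individual names and their respective unique study identification numbers, will be kept in a separate locked file".
- Section 7, item 3.B, under suicide risk: "As participants complete the data collection instruments, key personnel will review instruments and items for response values that indicate concern". The same paragraph continues: "If the disclosure is the result of one of the written items on the data collection tools", a specified member of staff telephones the participant.
- Section 7, item 3.B, under abuse: a youth's answers to survey items are one listed source of concern, and the resulting safety plan may include a report to Child Protective Services.
- Section 7, item 2.D concedes that mandatory reporting limits confidentiality.

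Some text points the other way. Section 6, item 5.3.1 says that students are told at consent that disclosed abuse will be reported. Section 7, item 2.D says the consent document states the duty to report child injury and imminent danger. Section 7, item 2.A says participants are told where and how data are stored.

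**The concern.** Students aged 15 to 18 are asked about sexual behaviour, drug use, life events and low mood. Immediately before those items they read that nobody can identify them, and at the end they read it again. If that is untrue, they decide what to disclose on a wrong understanding of who can see it. The safety procedure is also put in a difficult position: each time staff act on a survey answer, they break an assurance that the survey gave. The same survey supplies the primary outcome, so the students' trust in it matters to the trial as well as to them.

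**Working it through.** No figure in the plan lies behind this point, so the check is a comparison of passages. Each assurance is tested against the procedures.

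**1. Can anyone in the study identify a respondent?** Each student has a unique number. Survey data carry that number. The master sheet joins the number to a name. Whoever holds both can therefore identify the respondent, and Section 4.1 says certain staff hold the link while data are being collected. These are coded, re-identifiable data, which are not anonymous in the sense that the survey itself defines.

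**2. Does any procedure require a response to be associated with a name?** Yes, two do.

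| Procedure (Section 7, item 3.B) | Starts from | Ends in |
|---|---|---|
| Suicide risk | response values reviewed by key personnel | follow-up inquiry if judged necessary; a telephone call after a written disclosure |
| Abuse | survey answers among other sources | further inquiry; a safety plan that may include an agency report |

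Neither can run without going from an answer to an identified student. The closing assurance and these procedures cannot both hold.

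**3. Does the analysis need linked records?** Section 3.1.2 defines a dropout variable for each individual over four occasions, and its dropout model uses that person's previous and current outcome. Section 3.1.5 specifies autocorrelation within individuals. Both need the four surveys of one student joined. Taken alone, this requires only a code; the master sheet and the staff link in step 1 are what turn the code into a name.

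**4. What else are students told?** The consent process is described as covering abuse reporting, child injury, imminent danger and data storage, and staff go through the assent form with students (Sections 4.1 and 5.3.1). The available text does not say that students are told that staff review their answers or may telephone them. The consent and assent pages are not among the pages available, so this cannot be settled either way.

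**5. How many are exposed to the wording?** 456 students (Section 2.3.7) at baseline, 3, 9 and 12 months: 456 × 4 = 1,824 administrations at most, before attrition. This counts who reads the text. It is not a count of biased answers.

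**The case against.** The strongest reply is that consent and assent already disclose the limits. That stands in part. A reader might infer from the survey alone that students get no warning; the documents do not support that, because three places say that reporting duties or data storage are explained at consent. What remains is a conflict: the survey contradicts that explanation at the moment of answering.

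A second reply is that the survey only means that no name is typed into the form. One sentence of the Introduction can be read that way, but the definition it gives and the closing text go further.

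A third is that contacts would be rare. This is fair. The telephone call appears only under suicide risk, and the abuse report is only a possibility. The printed survey has no item on the student's own suicidal thoughts: life events 12 and 13 concern other people. Few items bear on abuse. Low-mood and life-event items are the likely triggers, and their yield is unknown. Rarity limits how often the promise is broken in practice; it does not make the promise true.

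Finally, the table of contents lists a tool revision history (Section 8) that is not in the available text, so the printed survey cannot be confirmed as the version used in the field.

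**Conclusion.** The survey's introduction and closing text are wrong as written and must be reconciled with Sections 4.1 and 7. The contradiction is certain on the available text, assuming that the printed survey is the one used. It applies to all 456 planned students at every round.

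A reader might go on to infer a bias in the primary outcome: students who learn that the survey was not anonymous answer later rounds differently, and this passes for an intervention effect. The design leaves room for it, since Section 2.3.5 places every student follow-up after that school has begun the intervention. But the documents do not show that it would happen, how many students would be affected, or which way answers would move. Condom use is collected as two past-month counts (items 5.5 and 5.6), so there is no single answer that simply flips. Distrust could equally lead a student to answer no at item 5.1, which skips the rest of that section, or to leave items blank; either removes the student from the measure. Setting an assumed share of changed answers against the 0.14 increase in Section 3.1.1 would therefore have no basis. The effect on condom use is of unknown size and direction, and the case for correction does not depend on it.

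**What to change.** Replace the three assurances in the survey's introduction and closing text with an accurate statement: answers are confidential, are stored under a code number, and can be linked to a name by a few study staff, including when an answer suggests risk of harm or abuse that must be reported. Check that the assent form says the same.

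If the text can be changed before baseline, use one version at all four rounds. Baseline was scheduled for March to June 2019 (Section 4.1), and the appendices hold a review-board memorandum dated September 30, 2020, so baseline may already have been collected. In that case correct the remaining rounds anyway, record which version each student saw at each round, and add a sensitivity analysis by version. That analysis has a limit: if every follow-up uses the new text, version cannot be told apart from follow-up, and some separation is possible only where follow-ups in an earlier wave used the old text.

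The cost is a text edit and a review-board submission. The downside is a possible small fall in disclosure. It would be expected to apply alike across rounds only if the change comes before baseline; a later change means that baseline and follow-up are answered under different assurances, which is why the version must be recorded.
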